Study objective:	To evaluate the efficacy and safety of preoperative short-course radiotherapy (SCRT) combined with subsequent chemotherapy (capecitabine and oxaliplatin) and PD1 inhibitor camrelizumab in patients with locally advanced rectal cancer (LARC).
Endpoints	
Primary endpoint: Pathological complete response (pCR) rate
 
Secondary endpoint: 3-year event-free survival rate R0 resection rate 3-year Overall survival rate Surgical complication rate Safety Quality of life

Sample size:	A total of 30 patients are planned to be enrolled in this study. The specific algorithm is as follows: this study will employ the single-arm design, with pCR rate as the primary endpoint. This study will adopt PASS 15 software, use tests for one proportion, and set $\alpha=0.025$ (one side) and $\text{power}=0.80$. The pCR rate of neoadjuvant therapy for locally advanced colorectal cancer was 15% previously, which is expected to reach 40% in this study. It is expected that 24 patients will need to be enrolled. Considering the drop-out rate of 20%, a total of 30 subjects should be enrolled
Study design	Patients with locally advanced rectal cancer (T3, T4a or 4b/N+) who are to receive preoperative neoadjuvant therapy: will receive preoperative local pelvic short-course radiotherapy. Radiotherapy will employ intensity-modulated radiation therapy, with a dose of 25 Gy/5 Fractions /1 week. One week later, a 3-week regimen of CAPOX chemotherapy combined with camrelizumab will be performed for 2 cycles. One week later, radical resection of rectal carcinoma will be performed. Postoperative adjuvant chemotherapy regimen will be determined by the doctor
Inclusion criteria:	
 (1) Age 18-75 years, male or female; (2) Histologically confirmed T3-4N0M0 or T1-4N+M0 rectal adenocarcinoma (AJCC/UICC TNM staging (8th Edition, 2017)); (3) with initial treatment (untreated with surgery, radiotherapy, chemotherapy or targeted therapy); (4) inferior margin ≤ 10 cm from the anal verge, (5) ECOG performance status score is 0-1; (6) With no severe hematologic disorder, cardiac, pulmonary, hepatic or renal dysfunction, or immunodeficiency; (7) Hemoglobin (Hb) ≥ 9 g/dL; white blood cell (WBC) $\geq 3 \times 10^9/L$; neutrophil (ANC) $\geq 1.5 \times 10^9/L$; platelet (Pt) $\geq 100 \times 10^9/L$; bilirubin < 1.5 times the upper limit of normal value; aspartate aminotransferase (AST) & alanine aminotransferase (ALT) ≤ 2.5 times the upper limit of normal value; serum creatinine ≤ 1.5 times the upper limit of normal value or creatinine clearance rate ≥ 50 mL/min; thyroid stimulating hormone (TSH) \leq ULN (If abnormal, T3 and T4 levels should be referred to simultaneously. If T3 and T4 are normal, the patient can also be enrolled); (8) Males or females with reproductive ability who are willing to use contraception in the trial; Women of childbearing potential who consent to practicing contraception during the period from giving informed consent to at least 23 weeks after the last dose of therapy; Male patients who consent to practicing contraception during the period from giving informed consent to at least 31 weeks after the last dose of the study drug; (9) Patients or their family members agree to participate in the study and sign the informed consent form; (10) No other severe cardiopulmonary diseases.
Exclusion criteria:	
 (1) Previous exposure to any anti-PD-1 or anti-PD-L1 antibody; (2) Lactating, pregnant women or women preparing for pregnancy;

Clinical Study Protocol

Version No.: V2.0

	
(3) Patients who need to be treated with corticosteroid (dose equivalent to prednisone of >10 mg/day) or other immunosuppressive agents within 2 weeks prior to study drug administration;
 
(4) Patients with concurrent autoimmune disease or a history of chronic or recurrent autoimmune disease;
 
(5) Patients with a history of thyroid dysfunction;
 
(6) Patients with a history or finding of cardiovascular risk;
 
(7) Patients with a known history of allogeneic organ transplantation and allogeneic hematopoietic stem cell transplantation; patients infected with HIV, or with active hepatitis B or C (reference for active hepatitis B: HBV DNA $\geq 10^4$ copies/mL; reference for active hepatitis C: HCV RNA $\geq 10^3$ copies/mL);
 
(8) Patients with a history of pneumonitis or interstitial lung disease (ILD, including previous and current medical history), such as interstitial pneumonia and pulmonary fibrosis, or have evidence of ILD on baseline chest CT or MRI;
 
(9) Patients who have allergic constitution or are allergic to multiple drugs;
 
(10) Patients with recurrent rectal cancer or a history of pelvic radiation;
 
(11) Patients with a history of inflammatory bowel disease;
 
(12) Patients complicated with severe infection;
 
(13) Patients with significant unstable mental diseases or other medical diseases that may interfere with the safety of the subjects, obtaining informed consent, or compliance with the procedures for the clinical study;
 
(14) Patients who participated in other clinical trials within 30 days before enrollment;
 
(15) Patients who are not suitable for participation in clinical trials in the opinion of the investigator.

Discontinuation criteria:	
Trial discontinuation means the clinical trial is not completed according to protocol and is prematurely discontinued. The main purpose of trial discontinuation is to protect the rights and interests of the subjects, ensure the quality of the trial, and avoid unnecessary economic losses.
 
(1) If serious safety issues occur during the trial, the trial should be discontinued in time;
 
(2) During the trial, major errors are found in the clinical trial protocol that make evaluation of drug efficacy difficult; or major deviations from the well-designed protocol are found in the implementation that make evaluation of drug efficacy difficult if the trial is to be continued;
 
(3) The sponsor requests to discontinue the trial (because of economic or management factors or others);
 
(4) The administrative department in charge rescinds the trial.

Dose design and treatment regimen:	
Patients will receive local rectal short-course radiotherapy. Radiotherapy will employ conformal or intensity-modulated radiation therapy, with a pelvic irradiation dose of 25 Gy/5 Fractions/1 week. Then rest for 1 week after radiotherapy and begin to receive neoadjuvant chemotherapy CAPOX and PD1 inhibitor for immunotherapy, for 2 cycles. One week after the completion of neoadjuvant therapy, a second evaluation on the primary lesions will be performed, and the surgical method is total mesorectal excision. Postoperative adjuvant therapy will be started 3-4 weeks after surgery, and the treatment regimen will be determined by the investigator. The efficacy of neoadjuvant therapy on postoperative specimens will be evaluated in accordance with Rectal Cancer Regression Grade. Treatment-related toxic and side effects will be evaluated as per CTCAE 5.0 toxic and side effects evaluation criteria.

Statistical method:	
This study will employ SPSS 16.0 statistical software package for analysis. EFS and OS will be analyzed using the Kaplan-Meier method and log-rank test.

Trial schedule:	
Estimated start time of the trial: Oct. 2019
 
Estimated time of enrollment completion: Oct. 2021
 
Estimated end time of the trial: Dec. 2025

Version No.:	V2.0

Clinical Study Protocol

Version No.: V2.0

List of Abbreviations

Abbreviations and statistics descriptions (English)

dMMR	Deficient mismatch repair protein
MSI	Microsatellite instability
mCRC	Metastatic Colorectal Cancer
PD-1	Programmed cell death protein 1
PD-L1	Programmed cell death ligand 1
MSS	Microsatellite stability
CTLA-4	Cytotoxic T lymphocyte-associated protein 4
OS	Overall survival
pCR	Pathological complete response
DNA	Deoxyribonucleic acid
WBC	White Blood Cell
RBC	Red Blood Cell
HGB	Hemoglobin
PLT	Platelet
ALT	Alanine aminotransferase
AST	Aspartate aminotransferase
Cr	Creatinine
BUN	Blood urea nitrogen
ESR	Erythrocyte sedimentation rate
AE	Adverse event
SAE	Serious adverse event
CRF	Case report form

1. Study Background

Rectal cancer is one of the most common malignant tumors in China, and its incidence rate is increasing year by year. Due to the atypical early symptoms of this disease, most of the patients are already in the locally advanced stage when they visit the doctor. The neoadjuvant chemoradiotherapy-based multidisciplinary synthetic therapy is the main treatment method for locally advanced rectal cancer at present. Preoperative radiotherapy can employ long-course regimen, in which conventional fraction radiotherapy and concurrent chemotherapy are used, or short-course radiotherapy with the dose of 25 Gy/5 Fractions. The former has a high tumor response rate, and the latter has low toxic and side effects and good tolerance. No difference is found in the local control rate between them. Delaying surgery for 4-8 weeks after short-course radiotherapy further increases the tumor response rate compared to surgery within 7 days. Recent studies have found that short-course delayed radiotherapy combined with neoadjuvant chemotherapy and delayed surgery can further improve the pathological complete response rate of tumor, and even show a better trend than the long-course concurrent radiochemotherapy, which have become a hotspot of current studies.

In 2015, it was first observed that metastatic colorectal cancer (mCRC) with molecular phenotype of deficient mismatch repair protein (dMMR) or microsatellite instability-high (MSI-H) could benefit significantly from monoclonal antibody immunotherapy with immune checkpoint inhibitor (programmed cell death receptor PD-1), which ushers in a MSI era in CRC immunotherapy. However, MSS/pMMR type colorectal cancer is not sensitive to immunotherapy, and even PD-L1 monoclonal antibody combined with MEK inhibitor or with antiangiogenic drugs does not bring clinical benefit. The Canadian study CCTG Co.26, reported in 2019 ASCO GI, is the first large phase II clinical study with positive results in MSS type mCRC patients, in which CTLA-4 monoclonal antibody combined with PD-L1 monoclonal antibody prolonged the OS of patients with refractory MSS type mCRC. Further, a study reported in 2019 ASCO combined nivolumab monoclonal antibody with standard long-course radiotherapy for preoperative treatment. The overall pCR rate was as high as 30%, and PD-L1 expression and the ratio of CD8+ lymphocytes/ regulatory T cells (CD8/Treg) could predict the efficacy of nivolumab monoclonal antibody. This study suggests that the immune checkpoint inhibitors are of great significance in neoadjuvant therapy for rectal cancer, especially their broad application prospect in MSS patients in the majority.

Radiotherapy can not only directly induce lethal DNA damage of tumor cells, making tumor cells acquire immunogenicity and producing anti-tumor immune response, but also generates remote effect through immune response. Mole first proposed and defined "abscopal" as the distant tissue with the same structure as the irradiated site in 1953. Since then, a large number of experiments have confirmed the existence of abscopal effect, especially the hypofractionated radiation therapy, which is more likely to trigger the abscopal effect. Considering that short-course hypofractionated delayed radiotherapy has equivalent efficacy with the long-course chemoradiotherapy in neoadjuvant therapy for rectal cancer and the potential immune activation effects brought by hypofractionated radiation therapy, we have reasons to believe that the short-course hypofractionated radiation therapy combined with neoadjuvant chemotherapy and immune checkpoint inhibitors may achieve better results in neoadjuvant therapy for rectal cancer.

2. Study Objective

Primary objective: The primary objective is to evaluate the efficacy of preoperative short-course radiotherapy combined with neoadjuvant chemotherapy and PD1 inhibitor in the treatment for locally advanced rectal cancer

Secondary objective: The secondary objective is to evaluate the safety of preoperative short-course radiotherapy combined with neoadjuvant chemotherapy and PD1 inhibitor in the treatment for locally advanced rectal cancer

Exploratory objective: To evaluate the relation of biomarkers (e.g. PD-L1 and MSI) in tumor tissues and/or blood to PD1 efficacy and pCR

3. Study Design

A prospective, single-arm, phase II clinical trial.

4. Selection and Withdrawal of Subjects

4.1 Inclusion criteria

- 1) Age 18-75 years, male or female;
- 2) Rectal cancer diagnosed by histology, with initial treatment (untreated with surgery, radiotherapy, chemotherapy or targeted therapy);
- 3) Locally advanced rectal lesion: T3, T4a or 4b/N+;

- 4) With no severe hematologic disorder, cardiac, pulmonary, hepatic or renal dysfunction, or immunodeficiency;
- 5) Hemoglobin (Hb) ≥ 9 g/dL; white blood cell (WBC) $\geq 3 \times 10^9$ /L; neutrophil (ANC) $\geq 1.5 \times 10^9$ /L; platelet (Pt) $\geq 100 \times 10^9$ /L; bilirubin < 1.5 times the upper limit of normal value; aspartate aminotransferase (AST) & alanine aminotransferase (ALT) ≤ 2.5 times the upper limit of normal value; serum creatinine ≤ 1.5 times the upper limit of normal value or creatinine clearance rate ≥ 50 mL/min; thyroid stimulating hormone (TSH) \leq ULN (If abnormal, T3 and T4 levels should be referred to simultaneously. If T3 and T4 are normal, the patient can also be enrolled);
- 6) Males or females with reproductive ability who are willing to use contraception in the trial; ECOG performance status score is 0-1;
- 7) Patients or their family members agree to participate in the study and sign the informed consent form;
- 8) No other severe cardiopulmonary diseases.

4.2 Exclusion criteria

- 1) Previous exposure to any anti-PD-1 or anti-PD-L1 antibody;
- 2) Lactating, pregnant women or women preparing for pregnancy;
- 3) Patients who need to be treated with corticosteroid (dose equivalent to prednisone of > 10 mg/day) or other immunosuppressive agents within 2 weeks prior to study drug administration;
- 4) Patients with active, known, or suspected autoimmune disease or a history of such disease within the past 2 years (patients with vitiligo, psoriasis, alopecia, or Grave's disease who do not require systemic treatment within 2 years, those with hypothyroidism who require only thyroid hormone replacement therapy, or those with type I diabetes who require only insulin replacement therapy can be enrolled);
- 5) Patients with a known history of allogeneic organ transplantation and allogeneic hematopoietic stem cell transplantation; patients infected with HIV, or with active hepatitis B or C (reference for active hepatitis B: HBV DNA $\geq 10^4$ copies/mL; reference for active hepatitis C: HCV RNA $\geq 10^3$ copies/mL);
- 6) Patients with interstitial lung disease (ILD, including previous and current medical history), such as interstitial pneumonia and pulmonary fibrosis, or have evidence of ILD on baseline chest CT or MRI;
- 7) Patients who have allergic constitution or are allergic to multiple drugs;
- 8) Patients with severe cardiac, pulmonary, hepatic or renal dysfunction, such as patients with decompensated heart, lung, kidney, liver or other major organs dysfunction, failure or poor glycemic control, or patients who are intolerant of chemotherapy;
- 9) Previous pelvic radiotherapy history;
- 10) Patients complicated with severe infection;
- 11) Patients with cognitive disorder, or poor compliance to chemotherapy as determined by the investigator;
- 12) Patients who participated in other clinical trials within 30 days before enrollment;
- 13) Patients who are not suitable for participation in clinical trials in the opinion of the investigator.

4.3 Removal criteria

Subjects who do not meet the inclusion criteria but are enrolled should be rejected, including: (1) misdiagnosis; (2) mistaken enrollment; (3) having not taken the medication; (4) having no evaluation records.

The reason of rejection should be explained for all rejected subjects, and their medical history in the study should be reserved for future reference. However, subjects who have received at least one treatment and have at least one safety record can be included in the safety analysis.

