4.4 Drop-out (withdrawal) criteria

(1) Adverse events; (2) lack of efficacy; (3) trial protocol deviation (including poor compliance); (4) trial discontinuation is determined to be necessary for subjects by the investigator due to medical concerns; (5) the patients themselves request to withdraw the trial.

When a patient drops out, the investigators must fill in the reasons for dropout in the case report form, try their best to contact the patient, and complete as much of evaluation items and related examinations. The investigators should fill in the pathography in the last time the patient is contacted, including the patient's last medication time and efficacy. Those who drop out due to adverse events, whether investigational product-related or not, should be recorded in the case report form.

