5.5 Concomitant medications

(1) During the clinical trial, except systemic intravenous chemotherapy according to the protocol, patients should stop using other drugs related to systemic treatment of tumor, including other chemotherapy drugs, targeted therapy, immunomodulators, Chinese patent medicine and other drugs that affect the efficacy;

(2) If there is a definite infection, or if the body temperature $\geq 38^{\circ}\text{C}$ and infectious fever cannot be excluded, antibiotics can be used and recorded in the CRF. The use of antifungal or antiviral drugs should also be recorded in the CRF.

(3) The subjects who receive concomitant medications that cause the difficulty of correct judgment of efficacy and safety should be treated as rejected subjects.

6. Medical Ethics Requirements

(1) The clinical trial protocol shall be approved by the ethics committee of the participating institution before it can be implemented. The approval document of the ethics committee on the clinical trial protocol will be copied to each clinical trial institution for the record.

(2) Informed consent form: The investigator should explain the objectives and process of the study to the enrolled subjects, and the informed consent form will be signed after obtaining the consent of the subjects.

This clinical trial will be conducted in accordance with the Declaration of Helsinki (2013 edition) and relevant Chinese Good Clinical Practice. The protocol should be reviewed and approved by the ethics committee of the hospital before the start of the trial. Any necessary modifications to the trial protocol during the clinical study should be reported to the ethics committee for the record.

7. Outcome Measures and Laboratory Tests

7.1 Medical history and physical examination:

Patients should be inquired by the doctor about their present and previous medical history in detail (including histories of allergy, cardiovascular disease, endocrine disease, respiratory system disease, and medication) before

being enrolled in the study. Systematic physical examinations and related laboratory tests will be performed before the trial and after the end of treatment. The medical history, physical examinations and laboratory tests results will be recorded in the CRF.

7.2 Laboratory Tests:

The enrolled patients will receive the following tests before treatment and after the end of the trial:

- 1) Blood routine test (HB + RBC + WBC), and coagulation function test;

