According to the previous studies, the pCR rate after preoperative CRT in patients with LARC is approximately 15%. We expected that the regimen of SCRT combined with subsequent chemotherapy and camrelizumab could increase the pCR rate from 15% to 40%. A sample size of 24 patients was required to provide at least 80% power to detect this estimated improvement, in one-sided χ^2 -test with a significance level of 2.5%, and a 20% dropout was considered, resulting in that a total sample size of 30 patients was planned for this study.

Statistical analyses were conducted using SAS® software (version 9.2, SAS Institute Inc, Cary, USA). Continuous variables were summarized using medians and ranges, and categorical variables were described using the frequency and percentage. Baseline and safety analyses were performed for all enrolled patients (intention-to-treat [ITT] population), and efficacy analyses were conducted for those who administrated at least 1 dose of camrelizumab (full analysis set [FAS] population). P value of less than 0.05 was considered statistically significant.

The exploratory objective is: to evaluate the relation of biomarkers (e.g. PD-L1 and MSI) in tumor tissues and/or blood to PD1 efficacy and pCR. Biomarker detection will be carried out with the treated tissue and/or blood obtained prior to treatment.

Continuous variables that conform to normal distribution will be expressed as mean +/- standard deviation, minimum value and maximum value, and those do not conform to normal distribution will be expressed as median; categorical variables will be described in frequency and percentage, and 95% confidence interval will be calculated if necessary. Mean values between the two groups will be compared by t test, and the rates between the two groups will be compared by chi-square test. Survival analysis will be performed by the Kaplan-Meier method. Comparison between groups will be performed by bilateral log-rank test. All tests are two-sided, and 0.05 is taken as the level of the tests.

9. Adverse Event Monitoring

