11.1 Data analysis set

Full analysis set (FAS): includes those who were administrated at least one dose of camrelizumab. When a primary efficacy indicator is missing, the previous result should be carried forward according to the principle of an intention to treat analysis. The missing values of comparability analysis and secondary efficacy indicators should not be subjected to data-carry-forward, and should be analyzed based on the actual data.

Per protocol set (PPS): includes subjects who meet the inclusion criteria, do not meet the exclusion criteria and have completed the treatment regimen, that is, those who meet the trial protocol, have good compliance and have filled all required sections of the CRF are included in the PPS analysis. In this trial, subjects who drop out after half of the treatment course due to aggravation should be included as invalid subjects in the PPS analysis.

Safety set (SS): subjects who have received at least one treatment and have actual safety assessment data. The missing safety data should not be subjected to data-carry-forward; some rejected subjects who are evaluable can be included, such as those with ages beyond the inclusion criteria, but excluding those who cannot be evaluated for safety due to the use of prohibited drugs. The number of subjects in the SS will be used as the denominator for the incidence of ARs.

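### The rejection rules in Protocol 4.3(4) and 5.5(3) conflict with the all-dosed efficacy set, so the same dosed patient can be in or out of the primary pCR denominator

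*Protocol*

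**What the plan says.** **Removal.** Protocol 4.3 says certain enrolled patients are to be rejected. Its list ends with "3) having not taken the medication; (4) having no evaluation records". The next paragraph allows treated patients with a safety record back into the safety analysis and names no other analysis. Protocol 5.5(3) gives the same status to a further group: "The subjects who receive concomitant medications that cause the difficulty of correct judgment of efficacy and safety should be treated as rejected subjects".

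**Efficacy population.** Protocol 8.2 states that "efficacy analyses were conducted for those who administrated at least 1 dose of camrelizumab" and calls this the full analysis set (FAS). Section 11.1 repeats the definition. Neither place makes an exception for rejected patients.

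**Missing primary outcome.** For the FAS, 11.1 asks that a missing primary result be replaced by the previous one, and cites the intention-to-treat principle.

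**Endpoint.** Under 8.2, pCR is ypT0N0, read from the resected primary tumour and the sampled nodes. It can only be observed after surgery.

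**The concern.** Take a patient who receives camrelizumab and never reaches resection. Under 8.2 and 11.1 this patient is in the primary denominator. Under 4.3(4), if missing pathology counts as a missing evaluation record, the patient is rejected. A dosed patient caught by 5.5(3) is in the same double position.

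For 4.3(4) the direction of the effect is known. A patient without a specimen cannot be a pCR, so deletion takes only failures out of the denominator. In a single-arm comparison with a fixed 15%, that raises the estimate directly, and no control arm shares the bias. For 5.5(3) the direction is not known, but the decision to reject rests on events after enrolment and on judgement.

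The carry-forward sentence shows that 11.1 expects patients with a missing primary result to stay in the FAS, but it gives them no usable value. No pCR assessment exists before surgery. The only earlier information is the baseline findings and the pre-surgical re-evaluation of the primary lesion described in the synopsis, and neither is a pathological response.

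**Working it through.** **Inputs (Protocol synopsis and 8.2).** The regimen is expected to change pCR as follows: "could increase the pCR rate from 15% to 40" (percent). The test is described as "in one-sided χ^2 -test with a significance level of 2.5" (percent). The size is given as "A sample size of 24 patients was required to provide at least 80% power to detect this estimated improvement". Allowing for 20% drop-out gives 30.

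**Step 1: reproduce the plan's figure.** I used the exact one-sample binomial and took the smallest r with P(Bin(n, 0.15) ≥ r) ≤ 0.025.
- n = 24: r = 8, type I error 0.0199, power P(Bin(24, 0.40) ≥ 8) = 0.8081.
- 24 / (1 − 0.20) = 30.

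Both figures reproduce. The sample size is not in question.

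**Step 2: rule with all 30 kept.** n = 30: r = 10, type I error 0.0097, power P(Bin(30, 0.40) ≥ 10) = 0.8237.

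**Step 3: the same data under the two rules.** Assume all 30 are dosed and that k patients, all non-pCR, are deleted. The protocol gives no value for k, so I take 0 to 6; six is the whole drop-out allowance (30 − 24). The p-value is P(Bin(30 − k, 0.15) ≥ x).

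| pCRs (x) | k = 0 | deletions | after deletion |
|---|---|---|---|
| 9 | 9/30 = 30.0%, p = 0.0278, fails | k = 1 | 9/29 = 31.0%, p = 0.0223, succeeds |
| 9 | as above | k = 3 | 9/27 = 33.3%, p = 0.0138, succeeds |
| 8 | 8/30 = 26.7%, p = 0.0698, fails | k = 3 | 8/27 = 29.6%, p = 0.0398, fails |
| 8 | as above | k = 6 | 8/24 = 33.3%, p = 0.0199, succeeds |

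With 7 pCRs the trial fails even at 7/24 (p = 0.0572). With 10 it succeeds even at 10/30 (p = 0.0097). Within this range the conclusion can change only at 8 or 9 pCRs.

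**Step 4: false success at a true 15% over all 30.** The critical value is 9 for denominators 25 to 29 and 8 for 24. Only non-pCRs are deleted, so the count of pCRs remains Bin(30, 0.15).

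| k | success if x ≥ | P(Bin(30, 0.15) ≥ x) |
|---|---|---|
| 0 | 10 | 0.0097 |
| 1 to 5 | 9 | 0.0278 |
| 6 | 8 | 0.0698 |

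**Step 5: what keeping everyone does to power.** If the 40% was meant for 24 evaluable patients and the other six count as non-pCR, the rate over 30 is 0.40 × 24/30 = 0.32. Power is then P(Bin(30, 0.32) ≥ 10) = 0.506.

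**The case against.** The best defence is that two sections state the efficacy population clearly, and that 4.3 is about patients enrolled in error. Its list stands under patients who fail the inclusion criteria. Removal from efficacy is inferred from the word for rejection. A patient who progresses before surgery would usually have some evaluation record, since 4.4 asks for last efficacy and as many examinations as possible at withdrawal. Item (3) of the 4.3 list agrees with the FAS if it means that no camrelizumab was given.

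Part of this stands. The upward bias depends on reading item (4) to include missing pathology, and item (3) is not in dispute. But having no evaluation records is not an inclusion criterion, so the opening words do not confine item (4). The inference about removal is also fair: 4.3 reopens only the safety analysis, and the safety set in 11.1 expressly readmits some rejected patients, while the FAS has no such clause.

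The size can also be challenged. The 20% covers drop-out for any reason, and patients lost before camrelizumab starts are outside the FAS under either rule. Six dosed, deleted non-pCRs is therefore the top of the range. For one to five, the false-success rate is only slightly above the nominal 0.025.

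The text does not support four stronger readings that a reader might infer:
- *Section 4.4 deletes non-responders.* It lists reasons such as "2) lack of efficacy; (3) trial protocol deviation (including poor compliance" for withdrawal, but removes nobody from an analysis set.
- *The per-protocol set (PPS) keeps only late failures.* The sentence "subjects who drop out after half of the treatment course due to aggravation should be included as invalid subjects in the PPS analysis" concerns drop-outs for aggravation. Eligible completers without pCR also remain as failures.
- *The PPS contradicts the FAS.* A narrower PPS is not a contradiction, and 8.2 assigns efficacy to the FAS.
- *Section 5.5(3) removes everyone on disallowed medication, mostly non-responders.* It covers only medication that hinders judgement, and nothing shows how those patients respond.

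**Conclusion.** The conflict is real and affects the primary denominator: 4.3(4) and 5.5(3) on one side, 8.2 and 11.1 on the other, with no rule on which prevails. Within 0 to 6 deletions, the trial's conclusion could change at 9 pCRs with a single deletion and at 8 pCRs with six. False success rises from 0.010 with all 30 kept to 0.028 (one to five deletions) or 0.070 (six).

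These figures assume that all 30 are dosed, that every deleted patient is non-pCR, that item (4) covers missing pathology, and that an exact binomial test is used. They show how far the choice of rule can matter and do not predict how many patients would be deleted. Because the contradiction lies in the protocol's own text, it should be resolved there before the primary analysis.

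**What to change.** 1. In 4.3 and 5.5(3), state that rejection under 4.3(4) or for concomitant medication does not remove a dosed patient from the FAS.
2. In 11.1, replace the carry-forward sentence for the primary endpoint with a rule that dosed patients without an evaluable specimen count as non-pCR. If both sentences stayed, they would compete.
3. Label the PPS analysis as supportive.
4. In the sample size paragraph, say whether the expected 40% refers to all dosed patients or only to those with an evaluable specimen.

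The cost is wording in 4.3, 5.5(3), 11.1 and the sample size text, and a lower pCR estimate than deletion would give (for example 26.7% instead of 33.3% with 8 pCRs and six deletions). It may also cost power: 0.82 if the 40% holds over all 30, but about 0.51 if it was meant for 24 evaluable patients and six others count as non-pCR. In the second case the sample size would need to be reconsidered, not only the wording.
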